It requires minimal cleaning, preparation and handling before or after patient use. Fully automated reports are also generated within minutes; thereby helping increase workflow efficiency and hopefully diagnose and treat patients in a more timely manner. Furthermore, it has the advantage of eliminating interscorer variability. This technology has the potential to be an accurate and safe alternative in diagnosing OSA in the younger age group, where the disease is known to be prevalent.

III. Preliminary Studies/Progress Report:

There have been validation studies which were mostly performed in adult patients. Weimin et al. studied 28 adults with suspected OSA who underwent an inpatient polysomnogram while wearing a WatchPAT 200. The study showed comparable accuracy in detecting OSA based on AHI (mean PSG score for events/hour was 23 ± 21.55 compared to a mean score of 25.00 ± 19.09 for the WatchPAT, $r=0.92$, $P<0.001$). It also provided a reasonably accurate estimation of sleep and wakefulness (agreement was $89\pm6\%$).³⁷ In another validation research using the WatchPAT200, Gan et al studied 20 patients with suspected OSA who also had simultaneous PSG and WatchPAT200 concurrently at the sleep lab. The study showed the WatchPAT being 100% sensitive when compared to PSG for detecting mild OSA and concluded that it is a good screening test for the undiagnosed general population. They study showed 100% specificity when compared to PSG for severe OSA suggesting that it is a good diagnostic test for people with a high suspicion of OSA.³⁸

A meta-analysis by Yalamanchali et al. on 14 studies assessing the correlation of sleep indexes between PAT devices and PSG in adults (aged >18 years). The researchers found high overall correlation of the RDI and AHI ($r=0.889$ [95% CI, 0.862-0.911]; $P<.001$). Studies comparing the RDI between PAT and PSG had a combined correlation of 0.879 (95% CI, 0.849-0.904; $P < .001$); those comparing the AHI, 0.893 (0.857-0.920; $P < .001$); and those comparing the ODI, 0.942 (0.894-0.969; $P < .001$).³⁶

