Summary statistics of basic demographics on the study population will be calculated. Wilcoxon signed rank test will compare median outcomes of interest (Total AHI, OAHI,etc) between WatchPAT 200 and PSG Lab testing. Spearman's correlation coefficient will be used to measure correlation between WatchPAT 200 and Lab testing. Bland Altman plots will graphically assess modality correlation. Sensitivity and specificity with 95% confidence intervals of WatchPAT 200 will be calculated for three cutoffs of the outcomes (<2, <5, and <10 events/hour) using the PSG lab study as the gold standard. Finally, test agreement on apnea categories will be assessed using Cohen's Kappa statistics fixing OSA diagnosis as dichotomized as none or mild (OAHI <2 events/hour) versus moderate or severe (OAHI \geq 5 events/hour) disease. Other analyses may be conducted on specific strata of participants, based on either patient age or BMI percentile.

Power and Sample Size

Power and sample size were calculated for the primary aim of the study using Power Analysis & Sample Size Software, PASS 15.0 (NCSS, LLC. Kaysville, Utah, USA). The primary aim is to assess whether the PatWatch device agrees with PSG laboratory studies in its ability to detect OSA. For the power analysis OSA diagnosis was dichotomized as non or mild (AHI<4.5) versus moderate or severe (AHI \geq 4.5) disease.

From previous clinical sleep study experience, (from personal review of PSG's performed at the Main Campus of Children's Hospital Colorado in the month of February 2017), investigators anticipate roughly 11 PSG sleep studies per month with about 2 patients diagnosed with OSA.

In a test for agreement between two raters using the Kappa statistic, a sample size of 120 participants achieves 80% power to detect a true Kappa value of 0.95 in a test of H0: Kappa \leq κ_0 vs. H1: Kappa $>$ κ_0 when there are 2 categories with frequencies equal to 0.82 and 0.18. This power calculation is based on a significance level of alpha = 0.05.

Investigators also wished to determine whether the difference of proportions of individuals detected to have OSA between testing modalities was no larger than 5%.

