A sample size of 147 participants achieves 80 % power at a significance level of 0.05 using a one-sided non-inferiority test of correlated proportions when the standard proportion is 0.18, the maximum allowable difference between these proportions that still results in non-inferiority (the range of non-inferiority) is 0.05 or 5%, and assuming the actual difference of the proportions is 0.0.

With 17 months enrollment and an enrollment rate of 80%, investigators anticipate enrolling 150 participants to ensure power >80% for each hypothesis test described above.

G. Summarize Knowledge to be Gained:

We hope to gain the knowledge that the WatchPAT 200 device will be able to detect OSA in children 4-12 years of age with comparable accuracy with an in-laboratory PSG.

H. References:

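### The kappa power calculation assumes an unsourced true kappa of 0.95 and an unstated null, so the claim of more than 80% power for each test is not supported unless agreement is near perfect

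*Combined protocol and SAP*

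**What the plan says.** Under Power and Sample Size (section IV.F), the primary aim is powered with a test of kappa: "a sample size of 120 participants achieves 80% power to detect a true Kappa value of 0.95". The hypotheses are written with a symbol where the null value should stand ("vs. H1: Kappa $>$ κ_0 when there are 2 categories"). The remaining inputs are "2 categories with frequencies equal to 0.82 and 0.18" and "This power calculation is based on a significance level of alpha = 0.05". The diagnosis is split at a single cut: "For the power analysis OSA diagnosis was dichotomized as non or mild (AHI<4.5) versus moderate or severe".

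A second calculation, for a non-inferiority test of paired proportions, asks for 147 children (standard proportion 0.18, margin 0.05, true difference 0, one-sided 0.05, 80% power). Enrolment is then set at 150 "to ensure power >80% for each hypothesis test described above".

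The Statistical Analysis plan in the same section describes the kappa differently. It is to be computed on OAHI "dichotomized as none or mild (OAHI <2 events/hour) versus moderate or severe", where the upper group starts at 5 events per hour.

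Section III cites no kappa for diagnosing OSA. It cites adult correlations. The meta-analysis gives "those comparing the AHI, 0.893 (0.857-0.920", and the 28-adult WatchPAT study gives r = 0.92. The only kappas cited (0.46 to 0.59) concern sleep staging.

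**The concern.** A power statement for a kappa test needs two values, the null and the assumed truth. Here the first is not printed and the second has no source. The assumed truth is also extreme: 0.95 leaves about two discordant children in the whole study. If actual agreement is good but short of that, the stated power does not apply, and readers would have been told that the primary agreement test was well powered when it was not. The cut used for the calculation is also not the grouping on which the analysis will compute kappa, so the power figure may not describe the planned statistic at all.

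**Working it through.** **Inputs from the protocol.** True kappa 0.95, N = 120, power 80%, alpha 0.05 and frequencies 0.82/0.18 (Power and Sample Size); 147 children with margin 0.05 (same section); r = 0.893 and 0.92 (section III). The null κ0 is not given.

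**Step 1: reproduce 120.** With equal margins π = 0.18, the large-sample variance of kappa times N is τ²(κ) = (1−κ)[(1−κ)(1−2κ) + κ(2−κ)/(2π(1−π))], with 2π(1−π) = 0.2952.
- τ²(0.80) = 0.20 × (−0.120 + 3.252) = 0.626, so τ = 0.7915.
- τ²(0.95) = 0.05 × (−0.045 + 3.379) = 0.167, so τ = 0.4083.
- N = [(1.645 × 0.7915 + 0.842 × 0.4083) / (0.95 − 0.80)]² = 120.3.

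A κ0 of 0.78 gives 100 and 0.82 gives 149, so a one-sided κ0 of 0.80 fits 120. Other sidedness or variance conventions return 120 with κ0 of about 0.71 to 0.77.

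**Step 2: what 0.95 means.** Discordance = 0.2952 × (1−κ). At 0.95 this is 0.0148: 1.8 children of 120, or 2.2 of 150.

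**Step 3: what the 147 calculation assumes.** By the simple large-sample formula, n = (1.645 + 0.842)² × d / 0.05², where d is the discordance. Setting n = 147 gives d = 147 × 0.0025 / 6.18 = 0.059, and kappa = 1 − 0.059/0.2952 = 0.80. At kappa 0.95 the same formula would ask for only 6.18 × 0.0148 / 0.0025, about 37 children. A score-type test back-solves to about 4.0% discordance, kappa 0.86. Either way, the two calculations assume different agreement for the same 18% positive rate.

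**Step 4: what the cited correlations suggest.** Assume a bivariate normal latent pair with 18% positive on both tests. Then kappa = (P11 − 0.18²)/0.1476, where P11 is the probability that both are positive.
- r = 0.893: P11 = 0.1315, kappa 0.67.
- r = 0.92: P11 = 0.1381, kappa 0.72.
- Kappa 0.95 needs r of about 0.9975.

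With lognormal margins the latent correlation becomes ln(1 + r·CV²)/ln(1 + CV²). A CV of 0.94 follows from the 28-adult study (21.55/23). With CV from 0.94 to an assumed 2.0, kappa is 0.71 to 0.76 at r = 0.893 and 0.75 to 0.80 at r = 0.92.

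**Step 5: power at N = 150 against κ0 = 0.80, one-sided.** Power = Φ{[√150 (κ−0.80) − 1.645 × 0.7915] / τ(κ)}.

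| True kappa | Power |
|---|---|
| 0.95 | 91% |
| 0.90 | 45% |
| 0.85 | 16% |
| 0.80 | 5% |
| 0.76 | 1.8% |
| 0.72 | 0.6% |
| 0.67 | 0.2% |

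**Step 6: sensitivity to the inferred null.** Take the lowest back-solved null, 0.713 two-sided (τ = 0.926), in the same power formula. At kappa 0.80, (12.247 × 0.087 − 1.96 × 0.926)/0.7915 = −0.95, which is 17%. At 0.90, (12.247 × 0.187 − 1.96 × 0.926)/0.572 = 0.83, which is about 80%. The two-sided null of 0.767 gives 6% and 48%.

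**Step 7: the planned categories.** Groups below 2 and at 5 or more leave 2 to <5 in neither. Suppose that band holds 10% to 30% of children (an assumption) and that pairs with either value in it are dropped. The bivariate normal model with r from 0.889 to 0.942 then gives kappa of 0.84 to about 1.0, on 58% to 84% of children (87 to 126 of 150).

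**The case against.** Power is always conditional on its alternative, and at the stated 0.95 a study of 150 has about 91%. That is correct. The objection is to calling the power assured when the alternative is unsourced and the same section's other calculation assumes less agreement.

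A reader might infer that the cited correlations imply a kappa of 0.67 to 0.80 and so contradict 0.95. The documents do not support that. A correlation fixes a kappa only under an assumed distribution and equal positive rates on both tests, and these are adult data carried over to children aged 4 to 12. The upper end, 0.80, needs a CV of 2.0 that the protocol nowhere gives. The evidence is also mixed: the 20-patient study reports 100% sensitivity for mild and 100% specificity for severe OSA, while a paediatric study reports a significant difference between PAT and PSG at ages 3 to 5.

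A reader might also infer that the null sits at or above any attainable kappa, so the test has almost no power. The null is a back-solve. Under the alternative nulls, part of the suggested range lies above it, and power at kappa 0.80 rises to about 17%. The planned <2 versus ≥5 grouping could also give a much higher kappa, though on fewer children.

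Finally, a reader might conclude that the trial is bound to read as negative, or is too small. No decision rule is attached to kappa: the analysis plan only assesses it, beside Wilcoxon, Spearman, Bland-Altman and sensitivity and specificity, in what the protocol calls a pilot. Enrolment is driven by the 147, not by the 0.95.

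**Conclusion.** The point stands in limited form and should be fixed; confidence is moderate. The absence of a source for 0.95, the missing null and the mismatch of cut-points can be read directly from the text. The conflict between 1.5% and about 5.9% discordance needs only the protocol's own figures and the simple formula for paired proportions.

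The size of the power shortfall rests on an inferred one-sided null of 0.80 and on the AHI 4.5 cut. On that basis, power at 150 is 91% at kappa 0.95, 45% at 0.90, 5% at 0.80 and under 2% at 0.76 or lower. Under the most favourable alternative null it reaches roughly 80% only at kappa 0.90. The claim of more than 80% power for each test therefore holds only if agreement is near perfect, and nothing cited establishes that. It does not follow that the device will fail or that the sample is inadequate for estimating agreement.

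**What to change.** - State the numerical value of κ0 and whether the test is one- or two-sided.
- Use the same index and the same single cut-point in the power and analysis sections, so that every child falls in one category.
- Replace the single 0.95 with power tabulated over kappa 0.65 to 0.95. Give a justification for any value singled out.
- Remove the unconditional statement that power exceeds 80% for each test.
- Report kappa with a 95% confidence interval and state its expected half-width at 147, 1.96 × τ/√147: about ±0.13 at kappa 0.80 (1.96 × 0.7915/12.12) and ±0.15 at 0.70 (1.96 × 0.943/12.12).

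The cost is a change of protocol and SAP wording. No extra children are needed. The downside is a less favourable stated power.

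### The 150 is sized on two hypothesis tests that the listed analyses do not carry out: kappa appears only as a statistic, on a different OSA split from the sized one, and the 5% paired test is not listed

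*Combined protocol and SAP*

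**What the plan says.** All of this is in section IV.F, Data Analysis Plan.

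**Power and Sample Size.** The aim being powered is agreement: "The primary aim is to assess whether the PatWatch device agrees with PSG laboratory studies in its ability to detect OSA". The split is given as "For the power analysis OSA diagnosis was dichotomized as non or mild (AHI<4.5" against 4.5 or more. Two calculations follow.

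- Kappa: "a sample size of 120 participants achieves 80% power to detect a true Kappa value of 0.95 in a test of H0", one-directional, with the null shown as "κ_0 when there are 2 categories with frequencies equal to 0.82 and 0.18". On the error rate: "This power calculation is based on a significance level of alpha = 0.05".
- Paired proportions: 147 children for 80% power in a one-sided 0.05 non-inferiority test, with standard proportion 0.18, margin 0.05 and true difference zero.

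The target of 150 is set "to ensure power >80% for each hypothesis test described above".

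**Statistical Analysis plan.** On differences: "Wilcoxon signed rank test will compare median outcomes of interest". Spearman correlation, Bland-Altman plots, and sensitivity and specificity with 95% intervals at three cut-offs come next. On categories, "test agreement on apnea categories will be assessed using" Cohen's kappa, with OAHI below 2 set against OAHI of 5 or more. No null value, alpha, bound or threshold accompanies this kappa. Neither the paired test nor the 5% margin appears among these analyses.

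**The concern.** A power statement has meaning only for the test it was computed for. Here the sized tests and the listed analyses differ in three ways: kappa is listed without its test, it is computed on another split, and the paired test is absent.

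The study hypothesis is that the device detects OSA as well as the laboratory study. Followed literally, the listed analyses give estimates and a Wilcoxon p-value. Wilcoxon looks for a systematic shift between methods. A large p-value can arise with poor agreement child by child, or from lack of power, so it cannot support the hypothesis. With κ0 unnumbered, the threshold for adequate agreement could also be chosen after the kappa is known.

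**Working it through.** **1. Can the 120 be reproduced?** Not from the printed inputs alone, because κ0 is missing. The inputs given are true kappa 0.95, frequencies 0.82 and 0.18, alpha 0.05 and power 80%. Assume equal margins and the usual large-sample variance of a two-category kappa. With sd(k) the standard deviation per child:

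N = [(1.645 × sd(κ0) + 0.8416 × sd(0.95)) / (0.95 − κ0)]²

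At κ0 = 0.80, sd(0.80) = 0.7915 and sd(0.95) = 0.4083. Then N = [(1.302 + 0.344) / 0.15]² ≈ 120.3, or 121 rounded up. Solving for exactly 120 gives κ0 = 0.800 one-sided or 0.767 two-sided. Since H1 is directional, 0.80 one-sided is the likely value, but that is an inference.

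**2. How much depends on κ0?** The observed kappa needed at N = 150 is κ0 + 1.645 × sd(κ0)/√150. For 0.80 this is 0.80 + 1.302/12.25 = 0.906.

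| κ0 (assumed, one-sided) | N for 80% power at 0.95 | Observed kappa needed at 150 |
|---|---|---|
| 0.60 | 36 | 0.74 |
| 0.70 | 58 | 0.83 |
| 0.80 | 121 | 0.91 |
| 0.85 | 221 | 0.94 |

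With 150 × 0.18 = 27 PSG-positive children, 4 discordant children give a kappa of 0.904 to 0.915 and 5 give 0.878 to 0.895. So κ0 = 0.80 tolerates about 4 discordant results in 150.

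**3. Are these figures for the planned kappa?** No. They describe a split of all children with 18% positive.

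| | Sized kappa | Listed kappa |
|---|---|---|
| Index | AHI | OAHI |
| Lower class | <4.5 | <2 |
| Upper class | ≥4.5 | ≥5 |
| Children in neither class | none | 2 to <5 |

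Leaving out the middle band changes both the number analysed and the prevalence. It also removes the children nearest the boundary, where disagreement is most likely. The documents do not give the share in that band, so the listed kappa's power cannot be computed.

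**4. Can the 147 be reproduced?** It also lacks an input, the proportion of discordant children ψ. With a Wald statistic, N = (1.645 + 0.8416)² × ψ / 0.05² = 6.183 × ψ / 0.0025, so 147 needs ψ = 0.059. A score statistic gives 147 at ψ = 0.040. With equal margins, kappa = 1 − ψ/(2 × 0.18 × 0.82) = 1 − ψ/0.2952, so these correspond to kappas of about 0.80 and 0.86. A kappa of 0.95 implies ψ = 0.0148, for which N would be 37 (Wald) or 96 (score). On these readings the two calculations assume different amounts of disagreement.

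**5. Could the 5% test stand in for agreement?** No. It compares the two overall proportions positive, which can match while individual children are classified differently. At ψ = 0.10 (kappa 0.66) with equal proportions, it would still pass 56% to 61% of the time at N = 150, and correctly so, because the proportions are equal.

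**6. What if both tests are required?** Taking κ0 = 0.80, 150 analysable children and symmetric discordance, simulated 2×2 tables give joint power of about 89% at kappa 0.95 (87% if the null standard error uses the observed margins). The kappa test is the limiting one at lower values. At 0.86, with sd 0.6715, its power is Φ[(12.25 × 0.06 − 1.302)/0.6715] = Φ(−0.84), about 20%, and joint power is about the same.

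**The case against.** The best defence is that the intention is readable. Cohen's kappa is a listed analysis. The power text sits under the same Data Analysis Plan heading, gives the paired test a margin, alpha and direction, and calls both items hypothesis tests. The protocol describes a pilot, and sensitivity, specificity, Bland-Altman plots and kappa remain interpretable as estimates. κ0 can be back-solved, and a symbol lost in document conversion cannot be wholly excluded, although it appears in both H0 and H1.

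Much of this stands, and it limits the point. Four stronger readings are tempting but unsupported:

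- A reader might infer that the plan has no criterion at all. It has one for the 5% question, in the power text; what is missing is an analysis that applies it.
- A reader might infer that 120 is wrong. It is uncheckable as written, and a plausible κ0 reproduces it.
- A reader might infer that passing either test would suffice, so that a device at the kappa null could easily earn the claim. No such rule is written. Agreement is named as the primary aim and the 5% question is introduced as an addition. Passing the 5% test when the true difference is zero is a correct result.
- A reader might infer that a non-significant Wilcoxon result will be presented as agreement. Nothing says so; the plan merely does not rule it out.

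What the defence does not answer is that kappa has no threshold in either section, the two splits differ, and the listed analyses omit the paired test. Pilot status does not settle it either, because the protocol itself claims power for each hypothesis test.

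**Conclusion.** The concern holds as a mismatch between sizing and analysis. The power above 80% attaches to two tests that the listed analyses do not run, and the primary agreement question has no numerical threshold. Across κ0 from 0.60 to 0.85, the observed kappa required at 150 moves from 0.74 to 0.94, so the unstated number largely decides the outcome.

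These figures assume equal margins at 18% positive, a one-sided 0.05 test, large-sample variances and 150 analysable children. The last is optimistic, because 150 is an enrolment figure and the plan excludes short, poor-quality or incomplete recordings. The figures do not carry over to the OAHI <2 versus ≥5 kappa. The value 0.80 is inferred and not documented. It should be settled before any data are analysed.

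**What to change.** In the Statistical Analysis plan:

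1. State the κ0 entered in the sample-size software, and the one-sided alpha. About 0.80 reproduces the 120; the sponsor should confirm it from the original run. Make the primary agreement analysis a one-sided 5% lower confidence bound for kappa compared with κ0.
2. Reconcile the two OSA definitions, then compute the primary kappa on the same dichotomy as the sample-size calculation, with every analysable child in one class or the other. If the sized split changes, rerun the calculation with the matching prevalence.
3. List the one-sided 5% paired-proportion non-inferiority test, with its statistic and assumed discordant proportion. State before analysis whether it is secondary or co-primary, and that it cannot establish agreement alone.
4. Label Wilcoxon p-values as descriptive.

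Items 1 and 4 are wording only and need no extra children. Item 2 is also wording if the sized split is kept. In item 3 the role is a design choice. Making the test secondary leaves the kappa calculation as the basis for power. Making it co-primary gives joint power of about 89% at kappa 0.95 but about 20% at 0.86, with κ0 = 0.80 and 150 analysable; nearly all of that loss comes from the kappa test itself.

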Data to be collected from all subjects include results of baseline/diagnostic polysomnogram (PSG) and sleep parameter indices (apnea-hypopnea index, etc.). Upon completion of the sleep study, the clinically indicated study will be scored by a physician as normal. The PSG will then be scored again by a single-point dedicated sleep technician research scorer to ensure consistent scoring methods between subjects and clinical sleep study scorers. The data collected by the WatchPAT 200 device will be scored through the WatchPAT 200 software installed on a local encrypted and password-protected computer. Additional information that may be collected includes medical history, medications, and basic demographic information.

D. Description, Risks and Justification of Procedures and Data Collection Tools:

The use of the WatchPAT 200 device has very low risk to the subject. This is a closed system that is worn on the wrist and finger that is not invasive to the patient. The device includes connections the EKG leads and other standard markers that are included in a clinical polysomnogram but are

optional and can be removed from the device between subjects. There is a slight risk of irritation of wearing the device as patients will most likely not be used to wearing someone on their wrists during their habitual sleep episodes.

E. Potential Scientific Problems:

There are no potential scientific problems at this time.

F. Data Analysis Plan:

Statistical Analysis plan

Data collected for a participant will be excluded from the analysis if any of the following: 1) WatchPAT 200 sleep time of less than 4 hours, 2) Lab test sleep time of less than 4 hours, 3) poor quality Lab test, consisting of a substantial portion of the Lab test not assessable, as determined by research staff occurred and 4) all WatchPAT 200 channel information not available from the study. The primary goal of the study is to validate and compare two sleep study modalities: 1) WatchPAT 200 and 2) Lab Testing sleep apnea.

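### Enrolling 150 does not secure more than 80% power for the non-inferiority test: it needs 147 analysed, and nothing is allowed for the four analysis exclusions

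*Combined protocol and SAP*

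**What the plan says.** All of the relevant text is in section IV.F.

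- **Kappa test** (Power and Sample Size): "a sample size of 120 participants achieves 80% power to detect a true Kappa value of 0.95", with category frequencies 0.82 and 0.18. The null value appears only as the symbol κ₀.
- **Non-inferiority test** (same section): "A sample size of 147 participants achieves 80 % power at a significance level of 0.05". It is one-sided, with a standard proportion of 0.18, a margin of 0.05 and a true difference of 0. No discordant proportion is stated.
- **Accrual**: "investigators anticipate roughly 11 PSG sleep studies per month", and then "With 17 months enrollment and an enrollment rate of 80" per cent.
- **Power claim**: "investigators anticipate enrolling 150 participants to ensure power >80% for each hypothesis test described above".
- **Analysis exclusions** (Data Analysis Plan): "Data collected for a participant will be excluded from the analysis if any of the following" applies. The four reasons are WatchPAT sleep time under 4 hours, laboratory sleep time under 4 hours, a poor-quality laboratory study, and "all WatchPAT 200 channel information not available from the study".

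Neither document part gives an expected exclusion rate, an inflation of the sample size or a rule for replacing excluded children.

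**The concern.** The power claim treats children enrolled as if they were children analysed, while the analysis plan in the same section says the two will differ. The 80% in the accrual sentence is an enrolment rate and is already used up in reaching 150, so it is not a reserve for unusable recordings.

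Some loss is foreseeable. All four rules apply to a single night in children aged 4 to 12 who wear an extra device on top of the full polysomnogram set-up, and the Background section itself notes that some children find polysomnography hard or frightening.

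At stake is the comparison with the stated 5% margin. A reader is told that its power exceeds 80%. If usable recordings fall short, a failure to show non-inferiority could reflect too few evaluable children rather than a real difference between the methods.

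**Working it through.** **1. Where 150 comes from.** 11 studies per month × 17 months × 0.80 = 149.6, which rounds to 150. The planned enrolment is the accrual projection with nothing added.

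**2. Slack on the plan's own sizing.**
- Non-inferiority: 150 − 147 = 3 children, 3/150 = 2.0%.
- Kappa: 150 − 120 = 30 children, 30/150 = 20%.

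**3. Chance of using up the slack of 3.** With exclusions binomial(150, rate), and the rates assumed because none is documented, P(more than 3 excluded) is 35% at a 2% rate, 66% at 3% and 94.5% at 5%.

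**4. Reproducing 147.** The discordant proportion d is not stated, so it was solved for.
- Wald form: N = d(z₀.₉₅ + z₀.₈₀)²/0.05². N = 147 gives d = 0.0594. At prevalence 0.18 this is close to kappa 0.80, where d = 2 × 0.18 × 0.82 × 0.20 = 0.0590.
- Score form (restricted maximum-likelihood variance under the null): N = 147 gives d = 0.0403.

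So 147 can be reproduced with a plausible discordance, and it is not in dispute here.

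**5. Power at smaller evaluable numbers.**
- Non-inferiority, Wald: power = Φ(0.05√(n/d) − 1.645) with d = 0.0594. For example, at n = 135: 0.05 × √(135/0.0594) = 2.384, and Φ(2.384 − 1.645) = 0.770.
- Non-inferiority, score: the same calculation with the restricted variance and d = 0.0403.
- Kappa: asymptotic Fleiss–Cohen–Everitt standard error, marginals 0.18, one-sided 0.05, true kappa 0.95. N = [(z₀.₉₅SE₀ + z₀.₈₀SE₁)/(0.95 − κ₀)]² gives 120 when κ₀ = 0.80, so κ₀ is also back-solved.

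| Evaluable (loss from 150) | Non-inferiority, Wald | Non-inferiority, score | Kappa |
|---|---|---|---|
| 150 (0%) | 80.7% | 80.9% | 90.6% |
| 147 (2%) | 80.0% | 80.0% | – |
| 146 (2.7%) | 79.8% | 79.7% | – |
| 143 (about 5%) | 79.0% | 78.8% | 88.7% |
| 135 (10%) | 77.0% | 76.3% | 86.1% |
| 120 (20%) | 72.6% | 70.9% | 80.0% |

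**6. Exact check of the score test.** Full enumeration at d = 0.0403 is more lenient: 83% at 147, 80% at 135 and 74% at 120. That discordance was calibrated to the asymptotic formula, so it does not return 80% at 147. Recalibrated so that exact power is 80% at 147 (d = 0.0451), power is 79.4% at 146, 79.9% at 143, 79.8% at 140, 76.9% at 135 and 71.2% at 120.

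**7. High-agreement case.** If kappa were 0.95, d = 2 × 0.18 × 0.82 × 0.05 = 0.0148. Score power at 120 is then 91% (exact 95%).

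**The case against.** The strongest reply has four parts.

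*The sentence is true if all 150 are analysed.* It is: power is then about 81% for non-inferiority and 91% for kappa. Nothing was miscalculated. What is missing is an allowance. But the claim is made for the number enrolled, and the same section says some of those children will not be analysed.

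*The affected test is the less central one.* This stands. The study calls itself a pilot, the section introduces its power calculation as being for the agreement aim, the kappa test comes first, and the non-inferiority test is added afterwards and does not appear in the Data Analysis Plan's list of analyses. That limits the consequence. It does not rescue a promise made for each test.

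*The size rests on two unknowns.* Also fair. The exclusion rate is assumed and the discordance is back-solved. The recalibrated exact test shows no sharp fall at the fourth exclusion: power is nearly flat down to about 140. At high agreement the test survives 20% loss. Against this, the plan states no discordance that would support the high-agreement case, and its published requirement is 147. At 10% and 20% loss the recalibrated exact figures (76.9% and 71.2%) agree with the approximate ones.

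*Exclusions may be few.* Studies are attended, a trained person places the device, and the eligibility criteria remove children expected to tolerate it poorly, all of which should lower losses. The fourth exclusion rule can also be read as covering only the loss of every channel. These points argue for stating an expected rate. They do not justify an implied allowance of 2%.

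**Conclusion.** The concern holds. On the plan's own sizing, more than 3 exclusions among 150 takes the non-inferiority test below its 80%, and a 5% exclusion rate would make that nearly certain (94.5%). The size is modest: about one point below 80% at 5% excluded, three to four points at 10%, and seven to nine at 20%. Put the other way, at 10–20% excluded the chance of missing non-inferiority when the two methods detect the same proportion rises from 20% to about 23–29%.

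These figures assume a true difference of zero, the stated margin and alpha, and a discordance back-solved from 147. Much higher agreement would remove the shortfall.

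The kappa test keeps at least 80% power down to 120 evaluable, given κ₀ = 0.80. That count leaves out a separate gap: the analysis wording is "dichotomized as none or mild (OAHI <2 events/hour) versus moderate or severe", with the second group starting at 5 events per hour, so children with OAHI from 2 to below 5 fall in neither category.

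**What to change.** Replace the claim of more than 80% power for each test with the power of each test at the expected evaluable number. Suggested wording:

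> Of 150 enrolled, we expect about X% to be excluded under the analysis rules, leaving N evaluable. At N, power is A% for the non-inferiority test (discordance d) and B% for the kappa test (κ₀ = k, true kappa 0.95).

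Illustrative values, with d back-solved from 147 and κ₀ = 0.80:
- N = 143: A about 79, B 89.
- N = 135: A 76–77, B 86.
- N = 120: A 71–73, B 80.

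This costs one or two sentences and adds no children, visits or months. The only downside is a slightly less favourable stated power for the non-inferiority test.

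If the investigators would rather protect the power than restate it, they could make 147 an evaluable target and enrol 147/(1 − X). That is 155 at 5% excluded, 164 at 10% and 184 at 20%. At 11 × 0.80 = 8.8 enrolled per month, these take about 17.6, 18.6 and 20.9 months. This is optional.
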